# 9.3 POPULATIONS FOR ANALYSES

The analysis for the primary and MRI-based secondary outcomes will be performed on all study completers. The analysis for the safety and tolerability secondary outcome will be performed on all participants who take at least one dose of tolebrutinib. Populations for exploratory post-hoc analyses will be defined at a later date.

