# 2.2.5 Co-treatment with anti-CD20 monoclonal antibodies

Since tolebrutinib treatment will be initiated within 6 months of each participant's most recent infusion of anti-CD20 monoclonal antibodies, which are normally given every 6 months and cause B cell depletion that persists even longer, there will be a period, lasting approximately 3–6 months, during which where both treatments are effectively combined. The effects of anti-CD20 are expected to gradually wane, such that by the second half of the 96-week duration of the primary study, participants will for all intents and purposes be taking tolebrutinib monotherapy. Samples for B cell counts are collected at various time points during this protocol.

Although no prior studies have examined specific co-treatment of tolebrutinib with anti-CD20 monoclonal antibodies, there is substantial published data that co-treatment with first-generation BTK inhibitors (such as ibrutinib) and anti-CD20 monoclonal antibodies (in particular, rituximab) is safe.

• In a Phase 2 study (NCT01520519) of 40 patients with high-risk chronic lymphocytic leukemia

(CLL), 6 cycles of ibrutinib 420 mg plus rituximab 375 mg/m2, followed by continuous ibrutinib, 13% had grade 3 infections, none had grade 4 or grade 5 infections, and only 1 had grade 4 neutropenia.

- A Phase 3 study (NCT01611090) of 578 patients with CLL or small lymphocytic leukemia (SLL) treated with a standard-of-care therapy, rituximab together with bendamustine, with the addition of ibrutinib 420 mg or placebo. At the 17-month interim analysis, progression- free survival was improved in the ibrutinib group (hazard ratio 0.23, p<0.0001), and safety signals were similar in both groups.
- A similar study (NCT02048813) subsequently randomized 529 patients with previously untreated CLL or SLL to either the same regimen of ibrutinib plus rituximab followed by ibrutinib alone or standard-of-care fludarabine, cyclophosphamide, and rituximab chemoimmunotherapy, again showing improved progression-free survival (hazard ratio 0.35, p<0.001) similar overall adverse event rate in the two groups, and fewer grade 3 infections in the ibrutinib plus rituximab group.
- Another study (NCT02007044) compared 420 mg of ibrutinib to ibrutinib together with rituximab in 208 CLL, with no difference in efficacy and similar rates of grade 3/4 treatment-emergent adverse events in both groups.

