#### 2.2.7 Rationale for outcome measures

**7-tesla MRI.** As described in Section 2.2.1, 7T MRI can detect iron deposition within activated macrophages/microglia at the edge of chronic active white matter lesions, which are the ultimate target of the therapy studied in this protocol. 7T MRI is also highly sensitive to the degree of parenchymal damage within lesions, and high-resolution data acquisition allows measurement of lesion size that is more accurate than at lower magnetic field strengths. The availability of 7T MRI therefore makes it possible to assess the effects of novel therapies on such lesions.

**Safety and tolerability.** Safety and tolerability will be assessed through patient interview and logging of adverse events (AE), as well as by lab work and imaging. Since tolebrutinib has not previously been used jointly with anti-CD20 antibody therapy in the treatment of MS, and it is not known if this combination could unexpectedly exacerbate disease inflammatory activity or predispose to development of opportunistic infections, safety monitoring by MRI will be interspersed between the 7T visits, with gradually decreasing frequency.

**Blood and CSF biomarkers.** We will collect blood and CSF samples for exploratory analysis of other potential biomarkers of tolebrutinib's efficacy. Techniques to be used may include (but are not limited to) flow cytometry immunophenotyping, cytokine/protein assessments, and single- cell RNA sequencing. Specific molecules to be assessed may include (but are not limited to); IL- 1 $\beta$ , IL-2, IL-6, IL-10, IL-12, IL-18, TNF, IFN $\gamma$ , IP-10/CXCL10, soluble CD27, CHI3L1/YKL-40, neopterin, and neurofilament light chain. Lumbar puncture is optional in the anti-CD20-only cohort.

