# **3** OBJECTIVES AND ENDPOINTS

OBJECTIVES	ENDPOINTS	JUSTIFICATION FOR ENDPOINTS					
Primary							
To evaluate the effects of 48 weeks of tolebrutinib 60 mg treatment on the paramag- netic rim of chronically in- flamed white matter lesions, as seen on 7-tesla MRI.	Per-participant proportion of lesions in which the paramagnetic rim has disappeared at the end of 48 weeks of tolebrutinib 60 mg treatment.	Paramagnetic rims indi- cate the presence of in- flammation and ongoing demyelination and axonal transection at the lesion edge. We have never ob- served complete disap- pearance of a chronic rim over the course of months, and the lesions under study will have been present for at least 6 months.					
Secondary							
To assess safety and tolera- bility of 96 weeks of tole- brutinib 60 mg (initial co- hort), or 48 weeks of treat- ment with tolebrutinib 60 mg and 96 weeks of treat- ment with tolebrutinib 120 mg (Cohort A), all follow- ing anti-CD20 antibody therapy.	Tabulation of adverse events.	There are no prior data regarding the specific combination of tolebru- tinib and anti-CD20 anti- bodies, or of BTK inhibi- tors and anti-CD20 anti- bodies in MS.					
To assess the possible repair of chronically inflamed white matter lesions in which in- flammation at the lesion edge has been modulated by tole- brutinib.	Changes in T1 relaxation time within paramagnetic rim lesions at the end of 96 weeks of tolebrutinib 120 mg, rela- tive to non-rim lesions. The analysis of T1 relaxation time changes will be per- formed by analysis of variance or mixed-effects models in study complet- ers. A threshold p-value of 0.025 will be taken as a significant change.	A reduction of the T1 relaxation time would be compatible with lesion repair.					
To assess the possible repair of chronically inflamed white matter lesions in which in- flammation at the lesion edge has been modulated by tole- brutinib.	Changes in size of paramagnetic rim lesions at the end of 96 weeks, relative to non-rim lesions. The analysis will be performed by analysis of variance or mixed-effects models in study com- pleters. A threshold p-value of 0.025 will be taken as a significant change.	A reduction in lesion size could indicate le- sion repair.					
Tertiary/Exploratory							

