### 8.4.4 Time Period and Frequency for Event Assessment and Follow-Up

The occurrence of an adverse event (AE) or serious adverse event (SAE) may come to the attention of study personnel during study visits and interviews of a study participant presenting for medical care, or upon review by a study monitor.

All AEs including local and systemic reactions not meeting the criteria for SAEs will be captured on the appropriate case report form (CRF). Information to be collected includes event description, time of onset, clinician's assessment of severity, relationship to study product (assessed only by those with the training and authority to make a diagnosis), and time of resolution/stabilization of the event. All AEs occurring while on study must be documented appropriately regardless of relationship. All AEs will be followed to adequate resolution.

Any medical condition that is present at the time that the participant is screened will be considered as baseline and not reported as an AE. However, if the study participant's condition deteriorates at any time during the study, it will be recorded as an AE.

Changes in the severity of an AE will be documented to allow an assessment of the duration of the event at each level of severity to be performed. AEs characterized as intermittent require documentation of onset and duration of each episode.

The investigator will record all reportable events with start dates occurring any time after informed consent is obtained until 7 (for non-serious AEs) or 30 days (for SAEs) after the last day of study participation. At each study visit, the investigator will inquire about the occurrence of AE/SAEs since the last visit. Events will be followed for outcome information until resolution or stabilization.

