# 9.1 STATISTICAL HYPOTHESIS

- Primary Endpoint: The per-participant proportion of lesions in which the paramagnetic rim has disappeared at the end of 48 weeks of tolebrutinib 60 mg treatment is >0.01.
- Secondary Endpoints:
  - Tolebrutinib 60 and 120 mg doses are safe and tolerable in the study population.
  - The T1 relaxation time has decreased in paramagnetic rim lesions at the end of 96 weeks of tolebrutinib 120 mg, relative to non-rim lesions.
  - The size of paramagnetic rim lesions has diminished at the end of 96 weeks of tolebrutinib 120 mg, relative to non-rim lesions.

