### 9.3.1 Evaluable for toxicity

All participants will be evaluable for toxicity from the time of their first treatment with tolebrutinib.

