### 9.4.4 Safety Analyses

To assess safety and tolerability, adverse events will be tabulated.

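### The planned safety analysis shows neither an adverse-event background on anti-CD20 alone nor the period of combined effect, and it leaves any 60 versus 120 mg reading confounded

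*Combined protocol and SAP*

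**What the plan says.** **Population.** Section 9.3: "The analysis for the safety and tolerability secondary outcome will be performed on all participants who take at least one dose of tolebrutinib". Section 9.3.1 agrees: "All participants will be evaluable for toxicity from the time of their first treatment with tolebrutinib".

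**Method.** Section 9.4.4 is one sentence: "To assess safety and tolerability, adverse events will be tabulated". It names no split by cohort, current dose or period, and no person-time. Section 9 states that there is no separate SAP.

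**Reason for the endpoint.** The justification column in Section 3 begins "There are no prior data regarding the specific combination of" and goes on to tolebrutinib with anti-CD20 antibodies. Section 2.2.7 gives the same reason ("Since tolebrutinib has not previously been used jointly with anti-CD20 antibody therapy in the treatment of MS") and raises disease activity and opportunistic infection as open questions.

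**Hypothesis.** Section 9.1 frames safety by dose: "Tolebrutinib 60 and 120 mg doses are safe and tolerable in the study population".

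**Timeline.** Section 2.2.5 expects about 3 to 6 months of combined effect. By the second half of the 96 weeks, "participants will for all intents and purposes be taking tolebrutinib monotherapy". Section 6.1.2.1 places the escalation of the four Cohort A participants at Week 48.

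**Data collected.** Section 8.4.4: "All AEs occurring while on study must be documented appropriately regardless of relationship". It makes no exception for the comparison cohort, which Section 1.3 schedules for visits at Weeks 24, 48, 72 and 96.

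**The concern.** Anti-CD20 therapy and BTK inhibition both plausibly affect infection and blood counts. If such events occur early, the planned table cannot show whether they resemble what patients on anti-CD20 alone experience, or whether they cluster while both agents are active. Those are the questions that the endpoint's justification raises.

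The same gap affects the doses. Because Section 9.1 names both, and Section 2.2.6 presents 96 weeks at 120 mg as new safety information, readers will compare them. All the overlap sits in the 60 mg period, so dose and anti-CD20 carry-over cannot be told apart in that comparison. Section 2.3.2 says the data may be useful in designing larger studies of higher-dose tolebrutinib, so a misread dose contrast could carry forward.

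**Working it through.** The documents give no sample size, power or precision figure for safety, so there is no stated safety figure to reproduce. The one interval in Section 9.2, for 2 of 7, belongs to the primary endpoint. It reproduces as the exact (Clopper-Pearson) interval, 0.0367 to 0.7096.

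**Inputs**
- 7 tolebrutinib participants: 4 escalated at Week 48, and 3 stay at 60 mg for a further 48 weeks (6.1.2.1).
- 96 weeks at 120 mg in Cohort A (1.1, 3).
- Comparison cohort of up to 10, followed to Week 96 (9.2, 1.3).
- Combined effect for about 3 to 6 months (2.2.5), taken here as 13 to 26 weeks from first dose.

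**Step 1: planned person-time, long-term extension excluded**
- 60 mg: 7 × 48 + 3 × 48 = 480 person-weeks.
- 120 mg: 4 × 96 = 384, an upper figure because Section 6.1.2.3 allows reduction to 60 mg.
- Comparison cohort: at most 10 × 96 = 960, assuming full enrolment and follow-up.

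**Step 2: where the overlap falls**
- 7 × 13 = 91 and 7 × 26 = 182 person-weeks, that is 91/480 = 19% to 182/480 = 38% of 60 mg time.
- Per participant: 13/48 = 27% to 26/48 = 54% of the first 48 weeks.
- Section 2.2.5 also says B-cell depletion outlasts the 6-month dosing interval. If overlap filled all 48 weeks, it would be 7 × 48 = 336 of 480 (70%).
- At 120 mg: essentially none, since escalation at Week 48 coincides with the start of the stated monotherapy phase.

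**Step 3: does the confounding have a known direction?** Suppose the monotherapy event rate is the same at both doses, and the overlap rate is k times that rate. The documents give no k; 0.5 to 3 is assumed. With O overlap person-weeks and w overlap weeks per person:
- Crude rate ratio, 120/60 = 480 / (480 + O(k − 1)).
- Raw count ratio per Cohort A participant, 96 weeks at 120 mg over 48 weeks at 60 mg = 96 / (48 + w(k − 1)).

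| k (assumed) | Rate ratio, O = 91 / 182 | Count ratio, w = 13 / 26 |
|---|---|---|
| 0.5 | 1.10 / 1.23 | 2.31 / 2.74 |
| 1.5 | 0.91 / 0.84 | 1.76 / 1.57 |
| 2 | 0.84 / 0.73 | 1.57 / 1.30 |
| 3 | 0.73 / 0.57 | 1.30 / 0.96 |

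With no true dose effect, rates favour 120 mg if overlap raises event rates and disfavour it if overlap lowers them. Raw counts make 120 mg look worse in every cell but one. The comparison is distorted, but the sign is not known.

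**Step 4: what the comparison cohort could show.** With no events, the two-sided 95% upper bound is 1 − 0.025^(1/n): 41% for n = 7, 60% for n = 4 and 31% for n = 10. Exact Fisher power for 7 versus 10 at two-sided 0.05 is about 6% for assumed proportions of 30% versus 10%, 28% for 50% versus 10%, and 64% for 70% versus 10%. This supports description, not testing.

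**The case against.** The formal objective is descriptive safety by dose after anti-CD20 therapy. The combination appears only as the justification, and no dose contrast is planned. Onset is recorded for every adverse event (8.4.4) and individual data are listed by time point (9.4.8), so with seven people a reader can place events in time. Section 1.1 mentions comparing the cohorts as exploratory, and Section 9.4.7 declines subgroup analyses at this size. This much stands: a reader might infer that the trial cannot address combination safety at all, and the documents do not support that. The data would allow a descriptive answer. What is missing is a specified one, since Section 9.4.9 leaves exploratory analyses post hoc and undefined.

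A reader might also infer that the tables will make 120 mg look safer than 60 mg. Step 3 shows why that does not follow: it needs a higher event rate during overlap, which no section gives, and a rate-based table, which no section plans.

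The strongest objection concerns the comparator. Those participants chose not to take tolebrutinib. Section 5.2.2 lacks the platelet, lymphocyte, hepatitis, HIV, infection and anticoagulant exclusions of Section 5.2.1, so the cohorts differ by design on risk factors for the events of interest. Their schedule has no ECG, interim MRI or interim safety laboratory tests. They also continue anti-CD20 treatment while it wanes in the tolebrutinib group. All of this stands. It limits the comparison to descriptive background, but does not justify omitting the data.

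**Conclusion.** The concern holds as a mismatch between the reason for the safety endpoint and the analysis specified for it. Sections 9.3 and 9.4.4 provide neither an anti-CD20-alone background nor a view of the combined period. About 19 to 38% of planned 60 mg person-time is overlap, against essentially none at 120 mg, so dose is confounded with overlap and with time on treatment.

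Selection adds to this, because the 120 mg experience comes from four people who had already completed 48 weeks at 60 mg. Section 9.2 reports that all seven reached that point, so drop-out does not separate the four from the three. Even so, 120 mg time begins only after a long tolerated period.

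The figures rest on full planned exposure and on 3 to 6 months equalling 13 to 26 weeks from first dose. No direction of bias should be claimed. The primary endpoint is unaffected. This is an inexpensive improvement to a stated analysis rule.

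**What to change.** Amend Sections 9.3 and 9.4.4 as follows.

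1. Tabulate the comparison cohort's adverse events beside those on tolebrutinib to Week 96. Give participants with events, person-time and exposure-adjusted rates. Repeat the table restricted to events ascertained at the shared 24-week visits.
2. Split tolebrutinib events by current dose and by period since first tolebrutinib dose, for example Weeks 0–26, 27–48 and after 48. Add a sensitivity split by the B-cell count from the nearest scheduled visit. No count is scheduled at event onset: Section 2.2.5 refers only to various time points, and Section 8.3 makes TBNK assays optional at 7T visits. A rule based on 6 months since the last anti-CD20 dose would work poorly, because Section 5.1.1 allows entry up to 6 months after that dose and some participants would then have almost no overlap.
3. State that 60 versus 120 mg is not a valid dose comparison, even on time after overlap.

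The cost is protocol wording and extra table columns, with no new procedures. Section 8.4.4 lists time of onset among the items recorded but not the visit at which an event was picked up, so confirm that the database holds this. State the downside beside the table: the comparison cohort is small (up to 10), self-selected, not subject to the tolebrutinib laboratory and infection exclusions, and monitored less, so the contrast is background only and no test should be attached.

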### 9.3.1 Evaluable for toxicity

All participants will be evaluable for toxicity from the time of their first treatment with tolebrutinib.

### 9.3.2 Evaluable for objective response

Only those participants who have received at least one dose of therapy and have had their disease reevaluated will be considered evaluable for response. These participants will have their response classified according to the definitions in section 9.4.

### 9.3.3 Evaluable Non-Target Disease Response

Not applicable.

# 9.4 STATISTICAL ANALYSES

9.4.1 General Approach

# 9.4.2 Analysis of the Primary Endpoint

The primary outcome is the per-patient proportion of lesions in which the paramagnetic rim has disappeared at the end of 48 weeks of tolebrutinib 60 mg/day, in comparison to the scan just prior to initiation of tolebrutinib dosing. Such participants can be in Cohort A or the Initial Cohort (combined analysis). Proportion of diminished/resolved paramagnetic rims is analyzed by investigators blinded to time point, reported descriptively, and compared to the assumption of no change off therapy via a binomial exact test. The analysis will be performed in study completers, and by definition no data will be missing. A threshold p-value of 0.05 will be taken as a significant change.

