## 1 PROTOCOL SUMMARY

## 1.1 SYNOPSIS

**Title:** A Phase 2 trial of the effect of tolebrutinib, a brain-penetrant Bruton's tyrosine kinase inhibitor, on chronically inflamed white matter lesions in multiple sclerosis

**Study Description:** The primary goal of this protocol is to test whether 48 weeks of treatment with tolebrutinib, an investigational, orally available, brain-penetrant, Bruton's tyrosine kinase (BTK) inhibitor, affects an imaging marker (the "paramagnetic rim") associated with chronically inflamed white matter lesions in multiple sclerosis (MS). In this rater-blinded but otherwise open-label study, 16 adults with MS who are on stable disease-modifying treatment with anti-CD20 antibody therapy and are within 6 months of their most recent dose, have at least one paramagnetic rim lesion on 7-tesla magnetic resonance imaging (MRI), and have developed no new white matter lesions or clinical relapses for at least 6 months, will initiate treatment with tolebrutinib and agree to forego further anti-CD20 or other disease-modifying therapy for the duration of the trial.

An initial 7 enrolled study participants started tolebrutinib at 60 mg/day ("Initial Cohort"). Of the Initial Cohort, participants (n=3), who had initiated tolebrutinib 60 mg will remain at 60 mg and not be escalated to 120 mg/day. The remaining participants (n=4) consented to Cohort A, who had initiated tolebrutinib 60 mg and previously escalated to 120 mg/day will remain at that dose.

Radiological, clinical, and biological outcomes are measured at 24, 48, 72, 96, and 144 (Cohort A) weeks, with additional interspersed visits for safety monitoring. Participants may subsequently continue treatment until tolebrutinib is marketed or commercial development halted. A comparison group of 10 participants who meet enrollment criteria but choose to stay on anti-CD20 therapy will also be enrolled. The primary outcome measure is disappearance of one or more paramagnetic rims from white matter lesions identified at baseline. Secondary outcomes include safety and tolerability and additional radiological outcomes. Exploratory clinical, radiological, and laboratory investigations are planned to study the mechanism of action of tolebrutinib and for biomarker development, and to compare the tolebrutinib and anti-CD20 cohorts.

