**Objectives:** *Primary Objective:* To evaluate the effects of 48 weeks of tolebrutinib 60 mg/day treatment on the paramagnetic rim of chronically inflamed white matter lesions, as seen on 7-tesla MRI.

Secondary Objectives: (1) To assess safety and tolerability of 48 weeks of treatment with tolebrutinib 60 mg and 96 weeks of treatment with tolebrutinib 120 mg (Cohort A) all following anti-CD20 antibody therapy. (2) To assess the possible repair of chronically inflamed white matter lesions in which inflammation at the lesion edge has been modulated by tolebrutinib.

**Endpoints**: *Primary Endpoint*: Per-patient proportion of lesions in which the paramagnetic rim has disappeared at the end of 48 weeks of tolebrutinib 60 mg.

Secondary Endpoints: (1) Adverse event tables. (2) Changes in T1 relaxation time within paramagnetic rim lesions at the end of 96 weeks of tolebrutinib 120 mg, relative to non-rim lesions. (3) Changes in size of paramagnetic rim lesions at the end of 96 weeks of tolebrutinib 120 mg, relative to non-rim lesions.

**Study Population:** Up to 10 adults with multiple sclerosis, targeting at least 7 participants who complete 48 weeks of therapy with tolebrutinib 60 mg in Cohort A. Up to 10 adults with multiple sclerosis who meet inclusion criteria but choose to stay on anti-CD20 therapy.

Phase: 2

[figure not shown]
**Description of Study Intervention:** Oral tolebrutinib 60 mg per day for 48 weeks (Initial Cohort), and a subgroup of patients already escalated to 120 mg (Cohort A), with optional long-term extension and follow-up.

**Study Duration:** 5 years

[figure not shown]
**Participant Duration:** 144 weeks (Cohort A) for primary and secondary outcomes, with optional long-term extension and follow-up.

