To assess the time course of an effect of tolebrutinib on the paramagnetic rims of chronically inflamed white matter lesions.	Proportion of paramagnetic rim le- sions in which the rim has diminished or disappeared at any time point, as- sessed by analysis of variance or mixed-effects models, which naturally handle missing data.	The time course of any effect of tolebrutinib on chronic neuroinflam- mation is unknown.
To obtain clinical data rele- vant to the efficacy of tole- brutinib.	Expanded Disability Status Scale (EDSS), 9-hole peg test (9HPT), 25- foot timed walk (25FTW), Scripps Neurological Rating Scale (SNRS), and symbol digit modalities test (SDMT), at baseline and every 24 weeks thereafter.	These are standard dis- ability scales that are used in the assessment of clinical progression in MS.
To obtain additional imaging data relevant to the efficacy of tolebrutinib.	Characteristics, including persistence, of paramagnetic rims at all time points (qualitative). Additional MRI measures to be determined. These analyses will be performed in NIH labs or through collaboration, either intramural or extramural.	To assess imaging cor- relates of reduced chronic neuroinflam- mation and/or tissue re- pair.
To obtain laboratory data rel- evant to the safety and effi- cacy of tolebrutinib.	Immune cell populations (e.g., macro- phages, lymphocytes, and subtypes thereof), cytokines (e.g., IL- 1ß, IL-6), and protein and other biomarkers of neuroinflammation and neurodegener- ation (e.g., neurofilament light chain, chitinase-3-like-1). Additional assays may also be developed and performed, such as the rate of repopulation of CD19+ cells. These analyses will be performed in NIH labs or through col- laboration, either intramural or extra- mural.	To assess laboratory correlates of reduced chronic neuroinflam- mation and/or tissue re- pair.

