## 4.2 SCIENTIFIC RATIONALE FOR STUDY DESIGN

Natural history data (both published and unpublished) indicate that in the absence of treatment, including treatment with anti-CD20 antibodies, paramagnetic rims are stable over periods substantially longer than the 96-week treatment duration in this study. Indeed, in unpublished work from the NIH, only 1 out of 29 individuals experienced subtle changes in the paramagnetic rim over the medium term (a period of  $\sim$ 5 years), meaning that we expect no untreated participants to experience changes in the shorter time period of observation in this study. The baseline-to- treatment design of this study, with a primary MRI outcome, is therefore justified.

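### Section 9.4.2 defines the primary outcome as rim disappearance, but its test sentence also admits diminished rims, an event the stated hypothesis does not cover

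*Combined protocol and SAP*

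**What the plan says.** **Event.** Section 9.4.2 begins: "The primary outcome is the per-patient proportion of lesions in which the paramagnetic rim has disappeared at the end of 48 weeks". The study description in the Synopsis agrees: "The primary outcome measure is disappearance of one or more paramagnetic rims from white matter lesions identified at baseline". The primary endpoint in Section 3 is, per participant, the "proportion of lesions in which the paramagnetic rim has disappeared at the end of 48 weeks of tolebrutinib 60 mg treatment". The hypothesis in 9.1 is that this quantity exceeds 0.01.

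**Powering and decision rule.** Section 9.2 sets a null of 0.01 and powers the study on 2 of 7 completers each losing at least one rim. It gives the interval (0.0367, 0.7096) and rejects if 2 participants have a lesion *change*.

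**Test.** Later in 9.4.2, the only sentence that names a test for the primary endpoint takes the proportion of "diminished/resolved paramagnetic rims is analyzed by investigators blinded to time point, reported descriptively, and compared to the assumption of no change off therapy", by an exact binomial test, with a threshold of 0.05.

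**Exploratory row.** Section 3 lists, as a tertiary or exploratory endpoint, the proportion of rim lesions in which "the rim has diminished or disappeared at any time point". It is to be analysed by analysis of variance or mixed models.

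**Context.** Section 9 states that there is no separate SAP. Section 7.1.2 removes from the primary analysis anyone off drug for more than 12 weeks. Section 9.2 reports that 7 participants had completed 48 weeks by May 2023, and the page header dates this version 6/21/2023.

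**The concern.** The test sentence and the outcome definition in the same section name different events. A rim that is fainter or less complete but still present is not a rim that has gone, and Section 3 treats the two as separate states by listing both words. Read literally, the test can count an event that neither the hypothesis in 9.1 nor the powering in 9.2 covers.

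The unit and the null move as well:

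- 9.4.2 reads most naturally as a proportion of rims compared with no change.
- 9.1 places 0.01 on a per-participant proportion of lesions, which is not a binomial count.
- 9.2 counts participants against 0.01.

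With 7 participants the primary conclusion turns on one or two events, so which event is counted can decide the result. Readers are blinded to time point, which protects the scoring of each scan. It does not settle which scored event enters the test.

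**Working it through.** **Inputs.** n = 7, null p0 = 0.01 and rejection at 2 participants (9.2); threshold 0.05 and exact binomial test (9.4.2); the two candidate events (first sentence and test sentence of 9.4.2).

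**Step 1: reproduce the plan's figure.** The Clopper-Pearson 95% limits for 2/7 are the 0.025 quantile of Beta(2, 6) and the 0.975 quantile of Beta(3, 5), which are 0.0367 and 0.7096. This matches 9.2, so 9.2 is a participant-level exact binomial calculation.

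**Step 2: p-values at n = 7, p0 = 0.01.** The p-value for x events is P(X ≥ x).

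- x = 0: p = 1.
- x = 1: 1 − 0.99^7 = 1 − 0.9321 = 0.068.
- x = 2: 1 − 0.99^7 − 7 × 0.01 × 0.99^6 = 0.06793 − 0.06590 = 0.0020.

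One-sided and two-sided exact p-values coincide here. One event does not reject; two do.

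**Step 3: apply both event definitions to the same data.** The 9.4.2 test sentence gives neither a participant count nor 0.01. A null of exactly no change would be degenerate: 1 − (1 − 0)^n = 0, so any single event would reject. The comparison therefore takes the event from 9.4.2 and the unit, null and n from 9.2.

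| Hypothetical Week 48 result | Disappearance only | Diminished or resolved |
|---|---|---|
| Two participants with a diminished rim, none with a rim gone | 0/7, p = 1 | 2/7, p = 0.0020 |
| One participant with a rim gone, one with a diminished rim only | 1/7, p = 0.068 | 2/7, p = 0.0020 |

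In both rows the choice of event reverses the conclusion at 0.05.

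**Step 4: type I error.** The 2-of-7 rule has attained error 0.0020 at a true rate of 0.01. It is 0.022 at 1/29 = 0.0345, the unscaled natural-history figure, and stays at or below 0.05 for any rate up to 0.053. The documents give no off-treatment rate for diminished rims above that.

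**Step 5: dependence of the cut-off on n.** The 7.1.2 exclusion could reduce n.

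- n = 6, one event: 1 − 0.99^6 = 0.059, not significant. Two events: 0.05852 − 6 × 0.01 × 0.99^5 = 0.05852 − 0.05706 = 0.0015. The cut-off stays at 2.
- n = 5, one event: 1 − 0.99^5 = 0.049, significant. The cut-off falls to 1.

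**The case against.** The strongest reply is that the controlling definition is evident. Disappearance is the event almost everywhere, including the hypothesis under test and the opening of 9.4.2, and it is the natural antecedent of the word change in the 9.2 rule. On that view the test sentence is loose wording, and a success claim with no rim gone would contradict 9.1. This is a fair reading, but the text does not secure it. Section 3 separates the two states. The test sentence is coherent as a test of change, because it compares diminished or resolved rims with no change. And 9.3.2 refers response classification back to the definitions in 9.4, where the conflict sits.

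Two further points stand in part. The null rests on natural history in which "only 1 out of 29 individuals experienced subtle changes in the paramagnetic rim over the medium term", so 0.01 is not plainly mismatched to a diminished-rim event. That does not make diminution the hypothesis. Sections 9.4.7 and 9.4.8 also promise descriptions and listings of individual participants, which would let a reader see whether rims had gone or only faded. That limits the harm but does not correct the test.

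The link to the exploratory endpoint should not be overdrawn. That endpoint applies at any time point and uses other models, so only the type of event is shared.

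**Conclusion.** The conflict is real and sits in the primary test: the wording of 9.4.2 admits an event outside the hypothesis in 9.1, and the closing words of 9.2 do not exclude it. Two diminished rims in two participants could move the result from p = 1 to p = 0.0020, and one could move it from p = 0.068 to p = 0.0020. These figures rest on combining the 9.4.2 event with the unit, null and n of 9.2; no single section prescribes that combination.

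A reader might infer three stronger things that the documents do not support:

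- *The plan is bound to declare success with no rim gone.* It permits this under one reading, but 9.1 and most of the text point the other way.
- *The false-positive rate is above 0.05.* This is not shown; it would need an off-treatment or misreading rate above about 0.053 per participant, and no such rate is given.
- *The looser wording was chosen with the results in hand.* All 7 had completed Week 48 before this version's date, but nothing says whether the reads were known. Sections 4.1 and 9.4.6 say that no interim analysis was planned or needed, which does not settle the question.

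**What to change.** - In 9.4.2, replace the diminished/resolved wording with *disappeared*. In the 9.2 rejection rule, replace the reference to a lesion change with *rim disappearance*.
- State one test in the Synopsis, Section 3, 9.1, 9.2 and 9.4.2: the number of completers in the primary analysis, after the 7.1.2 exclusion, with at least one baseline rim scored as disappeared at Week 48, by exact binomial test against 0.01 at p < 0.05. Say that this means at least 2 events when n is 7 or 6, and that the cut-off must be recomputed if exclusions reduce n further.
- Report per-participant lesion proportions descriptively and keep diminished rims exploratory.
- Make the change by a dated amendment with IRB approval, as the Statement of Compliance requires, and record whether the Week 48 reads were known. If they were, show the result under both event definitions.

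The cost is one amendment with wording changes in five places; no new scans or data are needed. The less favourable event becomes binding, and the per-participant lesion proportion is no longer the tested quantity. An amendment made after all 7 completed Week 48 cannot restore prespecification. It can only make the choice and its timing visible.
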